The target population of the "Be Yourself" program are adolescents between 11 and 15 years old in secondary schools in Santa Catarina, Nuevo León. Eligibility criteria include being enrolled in a public school with access to a computer lab and internet, residing with your parents, and having become sexually active or not. The sample will be of 150 randomly selected participants. Participation will be assessed using a filter questionnaire, and adolescents will be required to register on the program's website throughout the intervention, with the option to withdraw at any time.

Sample size

To determine the sample size, the nQuery Advisor statistical package will be used. The aim is to have 150 participants, of which 75 will belong to the CG and 75 to the EG, applying a simple random probability sampling. The sample will be calculated with an error level of .05, a power of 90%, a moderate effect size of .3, considering a loss of 20%.

Design of the Intervention "Be yourself"

The "Be Yourself" educational intervention was designed to prevent sexual risk in high school adolescents through self-determined motivation. Based on MACSPEA, the model of stages of change and competency-based learning uses a website (https://www.s-t-mismo.com/) and a chatbot for monitoring and activities (Table 2). The intervention consists of three sessions that address the prevention of adolescent pregnancy and the strengthening of skills. It includes hands-on activities,

role-plays, and interactive sessions on contraceptive methods, effective communication, and informed decision-making. To do this, specialized human resources and specific materials are required for its execution. Manuals were designed for the intervention and training of the facilitator, and activity guides for adolescents^{21,14-18}.

		Thematic content	Time	Components of the intervention
		Pre-test assessment app	40 min	Access to the "Be Yourself" page
ų	1.	What is self-determined motivation?: Discovering our dreams	60 min	Personal factors
First Session	1.	My Body: Anatomy, Physiology, and Sexual Health.	60 min	 Age of onset of sexual life Pregnancy Prevention
	2.	Navigating relationships: preventing unplanned pregnancy in adolescents.	60 min	Knowledge
	3.	Exploring Goals and Values to Prevent Unintended Pregnancies	60 min	Contextual factors
Second Session	4.	Be yourself: stop, think and act; Introduction to Troubleshooting	60 min	1. Sexual communication with parents

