	5.	Role-play: open dialogue about sexuality	60 min	 Sexual communication with friends Sexual communication with a partner
uo	6.	Navigating the Sea of Healthy Choices: Exploring Our Motivation	60 min	Psychological factors
Third Session	7.	My Space, My Decisions Exploring Our Needs	60 min	 Intrinsic and extrinsic motivation Satisfaction and frustration:
Thir	8.	Negotiating Healthy Choices: Preventing Pregnancy and STIs	60 min	autonomy, relationships and skills
Keep	9.	Building Self-Determined Motivation in Teens: Strengthening Session on Website and Chatbot	Continued individual	 Self-determined motivation, Behavioral Intent and Sexual Prevention Behavior
		Post-test assessment app	40 min	Access to the "Be Yourself" page
		Total, hours	10 hours 20	minutes more

Description of the control treatment

For the GC, two theoretical sessions are planned. In the first, an orientation on sexual health for adolescents will be offered through a one-hour PowerPoint presentation. Topics of anatomy, physiology, biological changes in adolescence and contraceptive methods will be addressed, highlighting their appropriate use and the prevention of teenage pregnancy. In the second session, also one hour, sexual health self-care skills will be developed, discussing the importance of self-care, self-respect, and informed decision-making. There will be a Q&A session to address concerns and reflect on how self-care contributes to a healthy and safe sex life.

Control measures

Randomization of participants

Participants will be thoroughly selected to represent the EG. Software will perform a simple, blinded randomization, assigning participants to control or experimental groups. Managers will be informed about the "Be Yourself" sessions, the dates and locations of which will be published on the website and communicated verbally. The sessions will be group, with individual activities on the website and through a chatbot.

Recruitment

Recruitment for the intervention will take place in February 2025, after the authorization of the educational authorities. Adolescents from the educational institution will be openly invited and their suitability will be evaluated according to inclusion criteria. Those selected will be recorded and assigned to control and experimental groups using an ID to ensure data integrity.

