With informed consent, participants will access the website and the chatbot for information and registration. After accepting, they will answer filter questions and receive a detailed explanation of the process. Those who do not qualify will receive a transparent explanation.

On the website, participants will record their personal data for effective communication and reminders. They will be informed about the royalties of the program at the end of the project, motivating them to participate in all activities. The information will be stored securely for one year.

Measurements and data collection

Data collection for the study will include the use of a specifically designed Personal Data Card, which will collect information about the sexuality, marital status, and education of the participants. A variety of scales will be used to measure aspects related to adolescent sexual health and behavior. The Sexual and Reproductive Health Knowledge Scale, Cronbach's alpha between .77 and .81²¹, will assess knowledge in these areas, while the Sexual Issues Communication Instrument, Cronbach's alpha from .89 to .95, will analyze sexual communication between parents, friends, and partners²². The Aspirations Index, alpha greater than .78 and .94, will measure life goals, and the Basic Psychological Needs Satisfaction and Frustration Scale will have alphas of .90 and .86²³.

[figure not shown]
The Behavior Regulation Questionnaire, adapted to the Mexican context, will assess behavior regulation to prevent pregnancy, with alphas between .66 and .93²⁴. Likewise, the Sexual Activity Intention Scale and the Sexual Activity Scale will assess sexual intentions and behaviors, respectively, with alphas from .83 to .88 and .74 to .86²⁵. The Sexual and Reproductive Health

[figure not shown]
Practices Scale, which examines pregnancy prevention behavior, with alphas of .92, .77, .81 and .87 in its different adaptations²⁶.

The "Scale for the Assessment of Change on Sexual Behavior in Adolescents"27 will be adapted and validated, ensuring its reliability. To assess the acceptability and feasibility of the "Be Yourself" intervention, aspects such as participant satisfaction, meeting expectations, and facilitator quality will be analyzed, along with participant recruitment, screening, randomization, and retention procedures.

Participant Retention Plan and Follow-Up

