The retention plan for the "Be yourself" intervention includes the delivery of T-shirts and caps with the logo of the program at the end, weekly sessions to avoid information saturation and a three-month follow-up. Data collection will be done through the website using digital tools to assess the effectiveness and acceptability of the program. The fidelity of the intervention will be ensured by training the principal investigator in self-determination theory and developing supporting manuals and guides. Figure 1 presents diagram CONSORT²⁰, which details the eligibility criteria, intervention, and evaluation of sessions before, after, and during follow-up at three months.

Ethical considerations

This study complies with the ethical regulations of the Regulations of the General Health Law, ensuring respect for the dignity and rights of the participants. The protocol has been approved by the Ethics and Research Committee of the Faculty of Nursing of the Autonomous University of Nuevo León, with registration number FAEN-D-2021. Informed consent will be obtained from the parents and assent from the adolescents. Participation will be explained in detail to parents and teens, including risks and benefits. The research will be suspended if there is a risk to the health of the participants or if they wish to withdraw²⁸.

Data analysis plan

The research will use statistical software SPSS version 26.0 for data processing. The analysis will begin with the Kolmogorov-Smirnov test to evaluate the distribution of the data and determine the suitability of applying parametric or nonparametric tests. The statistical analysis will include a descriptive level, using percentages, means, and standard deviation, to assess feasibility and acceptability. For hypotheses, inferential tests such as paired sample t-test, ANOVA, and Mann-Whitney U will be used to examine knowledge about pregnancy prevention, sexual communication, motivation, satisfaction of psychological needs, sexual intention, pregnancy prevention behavior, and stages of change in sexual behavior²⁹.

Table 3 describes the objectives and hypotheses proposed in this study, both descriptive and inferential statistics will be used

Objective	Analysis	Statistical
1 Examining feasibility	Descriptive	Measures of frequency, central tendency, and dispersion: percentages, means, ranges, Standard Deviation, confidence intervals, recruitment and retention rates.

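### The timetable of the experimental sessions goes on the website that both arms appear to use, with no separation by arm and no attendance check stated, so controls could see it and attend

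*Protocol*

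**What the plan says.** - **Assignment.** Under Control measures, Randomization of participants: "Software will perform a simple, blinded randomization, assigning participants to control or experimental groups".
- **Session notices.** The next sentence has managers informed of the Be Yourself sessions, "the dates and locations of which will be published on the website and communicated verbally". Table 1 gives Be Yourself to the experimental group only.
- **Who uses the website.** Population Characteristics and Eligibility Criteria: "adolescents will be required to register on the program's website throughout the intervention". Recruitment: "With informed consent, participants will access the website and the chatbot for information and registration". Neither sentence is limited to one arm.
- **Where outcomes are given.** Participant Retention Plan and Follow-Up: "Data collection will be done through the website using digital tools to assess the effectiveness and acceptability of the program". Measurements and data collection: "A variety of scales will be used to measure aspects related to adolescent sexual health and behavior". These are questionnaires that the adolescent completes.
- **When.** Table 1 has both arms measured before, at the end and at three months.
- **Control treatment.** Two one-hour theoretical sessions. The protocol does not say how these are announced.

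**The concern.** A website that serves as registration desk, information point and questionnaire platform for the whole sample is also the notice board for one arm's group sessions. A control pupil who returns to answer the end or three-month questionnaire, or to stay registered, may find when and where the experimental sessions take place.

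Two things are at stake. The first is contamination: controls who attend receive part of the experimental programme, and the estimated difference shrinks by an unknown amount. If attendance is not checked against allocation, the crossover is not recorded and cannot be described afterwards. The second is interpretation: the word *blinded* stands alone under Control measures without saying who is blinded. A reader may credit the self-reported outcomes with a protection they do not have.

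**Working it through.** **1. Can controls reach the notice?** The passages side by side:

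| Question | What the protocol states | Limited by arm? |
|---|---|---|
| Where are the experimental dates and places shown? | On the website, and verbally | No limit stated |
| Who registers on the website? | Adolescents in the programme's sample | No limit stated |
| Who gets information there? | Participants, after consent | No limit stated |
| Where are outcomes collected? | Through the website | No limit stated |
| Who is measured after allocation? | Both arms, at the end and at three months | Both arms |

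Only one website is described. Read together, these statements put controls on the site that carries the notice. Separate views by arm are neither stated nor excluded, so this is an inference from stated access.

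**2. Could controls attend?** Recruitment is by open invitation within the educational institution, and participants are assigned individually, so both arms appear to share a school. The logic model places the programme in the institution's computer room. The sessions are held in groups, and the retention plan makes them weekly. Participants have an ID, but the protocol describes no check of that ID against allocation at a session.

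**3. Which measurements are exposed?** Table 1 has a measurement before the intervention, and Table 2 puts the pre-test ahead of the first session. Attendance at experimental sessions can therefore affect only the end and three-month measurements.

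**4. How large could dilution be?** The documents give no crossover rate, so what follows is an illustration over an assumed range.

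*The planned size first.* Inputs from Sample size: error level .05, power 90%, effect .3, loss 20%, total 150. Neither the metric of .3 nor the sidedness is stated. With a two-sided test, the number per arm is n = 2 × (1.960 + 1.2816)² / d².
- If .3 is Cohen's f, then d = 2 × 0.3 = 0.6 for two groups. n = 2 × 10.507 / 0.36 = 58.4, so 59 per arm and 118 in total. 118 / 0.8 = 147.5, so 148, close to 150.
- If .3 is Cohen's d, n = 2 × 10.507 / 0.09 = 233.5, so 234 per arm, 468 in total, and 585 after loss. This does not give 150.
- A paired reading (standardised mean change 0.3) gives 117, or 147 after loss, also close to 150. The reading as f is therefore an assumption.

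*Then dilution.* If a share c of controls obtains the full experimental effect, the control mean moves by c × d and the contrast becomes d × (1 − c). With 75 × 0.8 = 60 completers per arm:

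power = Φ( d × (1 − c) × √(60/2) − 1.960 ), with √30 = 5.477.

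Worked case, d = 0.6 and c = 0.10: 0.54 × 5.477 = 2.958; 2.958 − 1.960 = 0.998; Φ(0.998) = 0.841.

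| c | Controls among 60 | Contrast kept | Power, d = 0.6 | Power, d = 0.3 | Sample size factor 1/(1 − c)² |
|---|---|---|---|---|---|
| 0 | 0 | 100% | 91% | 38% | 1.00 |
| 5% | 3 | 95% | 88% | 35% | 1.11 |
| 10% | 6 | 90% | 84% | 32% | 1.23 |
| 20% | 12 | 80% | 75% | 26% | 1.56 |
| 30% | 18 | 70% | 63% | 21% | 2.04 |

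A control who attends only some sessions, or responds only in part, dilutes less than the table shows.

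**The case against.** **The notice does not contradict the blinding.** A reader might infer that the protocol promises a blind and then breaks it. It does not. *Blinded* qualifies the assignment made by software, which can mean a concealed assignment, and a timetable published later is compatible with that. Nowhere does the protocol say that participants, facilitators or assessors are blinded. This objection stands; what remains is that the word is left undefined.

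**The notice is not the main cue.** Participation is explained in detail to parents and adolescents, and three multi-part sessions with role-play and a chatbot look nothing like two one-hour talks. Controls would probably recognise their arm with no timetable posted. This stands too: hiding the timetable would not restore blinding, and bias from arm awareness in self-report would largely remain.

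**Not every outcome is exposed.** It is tempting to say that controls know their arm before reporting anything. The baseline measurement precedes the intervention, and its order relative to randomization and to the notices is not stated.

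**Silence is not evidence.** The protocol does not say that the control sessions go unannounced, that the website is open to the public, or that anyone may walk in. The sentence names managers as those informed. Participants are registered and carry an ID, and a researcher and an assistant are listed as resources. This stands as a limit on how firmly the risk can be stated. It does not remove the risk, because publication on the website is stated and no safeguard by arm is.

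**The direction of bias is not settled.** Arm awareness could widen the contrast while attendance by controls narrows it. The documents support no figure for a shift in reporting, so none is given here.

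**Conclusion.** The point holds as a limited one. The protocol fixes a procedure that, as written, shows one arm's timetable to the other, with no separation by arm and no attendance check stated. Attendance by controls is a plausible consequence that the document neither reports nor prevents. It would dilute the contrast at the end and at three months.

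The size cannot be estimated from the document. The loss of contrast equals the share of controls who take up the full effect. The power figures rest on further assumptions: .3 read as Cohen's f, a two-sided test, 60 completers per arm and a simple two-group comparison.

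The conclusion rests on three readings of the text: that the website is common to both arms, that the arms share an institution, and that no view by arm exists because none is described. If any of these is wrong, the risk shrinks. The documents do not support a finding that controls are told their allocation by the notice, or that the trial breaks a promise of blinded participants. *Blinded randomization* can only mean concealed assignment here, since the visibly different arms make participant blinding unrealistic.

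**What to change.** - **Session notices.** Do not post the experimental timetable on the shared website. Send each participant only their own arm's session times, using the contact data that the website already records for communication and reminders.
- **Attendance.** Check each attendee's ID against the allocation list at every session and record any crossover. The pilot already sets out to examine feasibility, so the observed crossover rate would be a useful result.
- **Wording.** Replace the phrase about blinded randomization with: concealed computer allocation; participants and facilitators are not blinded. The first half assumes that concealment is what the software step provides, which the team should confirm. Carry the limitation into the conclusions on the self-reported outcomes.

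The cost is a small messaging task, an ID check at sessions and two sentences of protocol text, with slightly less publicity for the experimental sessions. These steps reduce contamination and make it visible; they do not blind the participants.

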I	Problem	Self-determined motivati	on fo	r adolescent pregnanc	cy pre	evention.		
	Meta That adolescents achieve the stage of action and maintenance of self-determined motivation to prevent adolescent pregnancy.							
Ju	ıstificatio n					n for the Prevention of Pregnar e Competency-Based Learnin		
	As	ssumptions		Entrance Resources		Outputs Activities	Outputs	Results
a.	may not recog pregnancy if t	the precontemplation stage gnize themselves at risk for they lack awareness of the usequences and risks.		Human: Researcher, research assistant Financial:		Session 1: Getting to know yourself, steps to achieve your "Be Yourself" goals Knowledge and awareness	 "Be Yourself" faithfully implemented. Videos viewed on 	Primary 1.Increase in Self-Determined Motivation Indices to Prevent Adolescent Pregnancy (H5).
b.	If teens don't hat pregnancy pre	ave enough knowledge about evention, condom use, and they're likely to stay in the		Operating budget for the production of the material. Space: Computer		1. What is Self-Determined Motivation?: Discovering Our Dreams 2. My Body: Anatomy,	 web platform Participants discuss condom use and 	 2.Increased Level of Knowledge about Pregnancy Prevention (H1). 3.Improved Communication on Sexual Issues (H2.
c.	A lack of toward abstine	self-determined motivation ence and condom use can escents' transition to the		room of the educational institution Materials: didactic		Physiology and Sexual Health. Problem solving, negotiation.	negotiation 4. There is a discussion about abstinence and	 4. Change in Life Goals (H3): Significant increase in orientation toward intrinsic life goals (such as personal and academic development).
d.	A lack of se parents, friend difficult for te stage, where	exual communication with ds, and partners can make it evens to move into the action to they are expected to anges in sexual behavior and		and recreational materials for the intervention. Access to the web platform		3. Navigating Relationships: Preventing Unwanted Teen Pregnancy. Session 2: Building Personal Commitments: Conduct,	prevention of pregnancy 5. Negotiation and rejection skills are practiced	 5. Satisfaction of Basic Psychological Needs: autonomy, relationships and competence. (H4). Secondarys Intention to Risk and Protect (H6):

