- 2. Detailed knowledge about the correct use of condoms and awareness of their importance in protecting against STIs are key results in promoting sexual health.
- 3. Improved negotiation skills are reflected in an increased ability to communicate and reach agreements, accompanied by the development of empathic skills and a broader understanding of others' perspectives.

Session 2: Building Personal Commitments: Conduct, Behavior, and Sexual Communication

- 1. Exploring Goals and Values: Teens identify personal goals and strategies to prevent pregnancy through hands-on exercises and role-playing.
- 2. Problem-solving: Communication skills and informed decision-making are developed in relationships, focusing on values and limits.
- 3. Role play: Open communication about sexuality is practiced with parents, friends and partners, evaluating progress and challenges.

Session 3: Empowerment and Concrete Actions: improving negotiation and rejection skills

- 1. Teens will create a "Negotiation and Rejection Skills Guide." This guide would include specific strategies learned during the session, practical tips for coping with challenging situations in preventing unintended pregnancy.
- 2. Adolescents participate in the "Motivational Campaign on Sexual Health", promoting the importance of personal empowerment, informed decision-making and self-motivation on issues related to sexual health. This campaign could include inspirational messages, testimonials, and helpful resources to foster self-determination among peers.
- 3. "Interactive Simulation with Chatbot", which simulates situations of negotiation and rejection in the context of sexual relations and prevention of unplanned pregnancy, allows adolescents to practice and reinforce the skills learned, providing instant feedback on their choices and decisions.

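### Both arms share one school and one website, and the protocol neither closes nor measures the routes by which controls may meet intervention content before the 3-month measurement

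*Protocol*

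**What the plan says.** **Setting.** The Recruitment section states: "Adolescents from the educational institution will be openly invited". The logic model's resources place delivery in the computer "room of the educational institution". The population section speaks more broadly of adolescents "in secondary schools in Santa Catarina, Nuevo León".

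**Unit of allocation.** Under Randomization of participants: "Software will perform a simple, blinded randomization, assigning participants to control or experimental groups". No class or school is named as the unit.

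**Campaign.** The second product listed for Session 3 is a motivational campaign on sexual health in which adolescents take part. It promotes empowerment, informed decisions and self-motivation, and the text adds: "This campaign could include inspirational messages, testimonials, and helpful resources to foster self-determination among peers".

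**Website and chatbot.** The Recruitment section says that, with consent, "participants will access the website and the chatbot for information and registration", without distinguishing the arms. The same platform carries active content. Table 2 places a strengthening component on self-determined motivation on the website and chatbot, and the logic model lists videos on the web platform and a chatbot simulation.

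**Timing and outcome.** Table 1 measures both arms before, at the end and at 3 months. The retention plan has "weekly sessions to avoid information saturation and a three-month follow-up". The first primary result in the logic model is self-determined motivation (H5).

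**The concern.** When individuals in one school are randomised, pupils of both arms meet every day. Some informal leakage is then unavoidable, and a pilot may reasonably accept it in exchange for avoiding cluster randomisation. The point here is narrower. The protocol describes two specific channels, a campaign with resources for peers and a website with chatbot, and sets no boundary between the arms on either. The section titled Control measures deals with randomisation and recruitment logistics only.

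Both channels bear on the construct named first among the primary results. If part of the intervention's effect reached controls, the difference between arms would move towards zero. Because exposure is not recorded, the investigators could not say afterwards how much of a small difference was due to spillover. That matters both for the stated aim of preliminary efficacy and for deciding whether a later trial needs clusters.

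**Working it through.** **Step 1: do the arms share an environment?** Recruitment and the logic model both refer to a single institution. If the plural in the population section were taken to mean several schools, simple individual randomisation would still be expected to place both arms in each school. The shared setting holds on either reading.

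**Step 2: can content cross before outcomes are measured?** The campaign is a Session 3 product, but it has no date and no line in Table 2. What can be said is that it stems from a session held before the 3-month measurement and that nothing defers it beyond that point. The website and chatbot are in use from registration onwards.

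**Step 3: reproduce the planned size.** Inputs from the Sample size section: error level .05 (two-sided assumed), power 90%, effect size .3 (metric not stated), loss 20%, total 150 as 75 + 75.

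- Read .3 as Cohen's f for two groups, so d = 2f = 0.6.
- Normal approximation: n per arm = 2(1.960 + 1.282)² / 0.6² = 58.4, so 59. The exact t-test gives 59.35, so 60.
- Total 2 × 60 = 120, and 120 / (1 − 0.20) = 150. This matches the protocol.

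Other readings:

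- A paired standardised difference of .3 gives 117 to 119 in total, or 147 to 149 after loss. That is close, but it is not a comparison between arms.
- Cohen's d = .3 between arms gives 234 per arm by the normal approximation, or 585 in total after loss. That does not match.

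**Step 4: effect of dilution.** Let c be the share of the intervention effect that reaches controls on average. The documents give no value, so c is assumed and shown as a range. The diluted effect is d(1 − c). With n = 60 completers per arm the noncentrality is d(1 − c)√(n/2), where √30 = 5.477. The factor by which the sample must grow to offset dilution is 1/(1 − c)².

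| Assumed c | Diluted d | Noncentrality | Power (exact t) | Sample-size factor | Total N for 90% power, with 20% loss |
|---|---|---|---|---|---|
| 0 | 0.60 | 3.29 | 90.3% | 1.00 | 150 |
| 10% | 0.54 | 2.96 | 83.5% | 1.23 | 185 |
| 20% | 0.48 | 2.63 | 74.1% | 1.56 | 233 |
| 30% | 0.42 | 2.30 | 62.6% | 2.04 | 303 |

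**Step 5: sensitivity to the effect-size reading.** If .3 were Cohen's d, the proportional shrinkage would be the same, but power with 60 completers per arm would start at 37.1% and fall to 25.6% at c = 20%. The loss of power therefore depends on the reading of .3, while the direction of the bias does not.

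**The case against.** The strongest reply is that the text does not describe exposure of controls. Pupils take part in the campaign, and nothing says that they run it. Its contents are what it could include. Peers is undefined and, since the sessions are held in groups, may mean fellow EG members. The facilitator manuals and activity guides, which are not shown, may settle the audience. All of this stands. A reader might infer that the plan itself delivers the intervention to controls, or does so before the post-test. The documents support neither: the audience is open, the campaign is undated, and the website passage grants access for information and registration without saying that controls receive the sessions' content.

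It is also fair to say that the power figures rest on an unstated metric and that no document supports 10% to 30%. An optional campaign may carry far less of the effect of a programme lasting some ten hours. The figures are illustrations, not estimates.

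A third argument is that repeated measurement in both arms would reveal a control group that improves. This holds only in part. The control arm has two one-hour sessions of its own on related topics, so improvement there could come from those sessions as well as from spillover. Without an exposure question the two cannot be separated.

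What the reply does not remove is that the protocol leaves two named routes open and unmeasured. The campaign's audience, access to the platform and the content of questionnaires are design matters that a statistical analysis plan would not normally settle.

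**Conclusion.** The point holds as a possible and unmeasured exposure. Individual randomisation within one institution, a campaign for undefined peers, and shared access to a website and chatbot together mean that controls may meet active content before the 3-month measurement. Any spillover would bias the contrast in self-determined motivation towards zero.

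Its size is unknown. Under three assumptions (.3 read as Cohen's f, a two-sided test, and 60 completers per arm), dilution of 10% to 30% would lower power from about 90% to between about 83% and 63%. This does not make individual randomisation the wrong choice for a pilot, and it does not by itself call for clusters or more participants. It is an inexpensive improvement that should be made before recruitment.

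**What to change.** 1. State in the protocol that campaign materials, and intervention content on the website and chatbot, are available only to EG participants until the 3-month measurement is complete. Controls use the site only for registration and questionnaires.
2. Add two items at post-test and at 3 months, put to all participants: whether they saw campaign material, and whether they saw intervention content on the website or used the chatbot for it.
3. Report control-arm exposure as a feasibility outcome, beside the recruitment, screening, randomisation and retention procedures already planned.

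**Cost.** Protocol wording, two questionnaire items and a narrower campaign during the trial. The protocol describes no access rights by arm, so the site may also need a small configuration change. The sample size and the unit of randomisation stay as they are.
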